STUDY PROTOCOL & STATISTICAL ANALYSIS PLAN

STUDY TITLE: ADAPTING AND IMPLEMENTING TEAMSTEPPS IN SCHOOL MENTAL HEALTH

NCT04440228

AUGUST 20, 2025

Project Aim 3 - Explore the feasibility, acceptability, and utility of TeamSTEPPS plus the strategies generated in Aim 2 on inter-professional collaboration, teamwork, and outcomes in schools.

PROTOCOL

Procedure. The primary implementation outcomes are feasibility and acceptability of the adapted TeamSTEPPS, consistent with recommendations for selecting appropriate outcomes for pilot phase research. We also explored collaboration and teamwork, assessed via self-report and observation, behavioral and educational outcomes for students, and potential contextual predictors of implementation which will allow us to identify measures that are sensitive to change for future trials. Inter-professional collaboration, which has been identified as a key factor in quality school mental health promotion, is assessed via self-report and observation. We will collect self-report data at baseline (i.e., before engagement in TeamSTEPPS) and for the school year following participation at two time points each school year (fall, spring).

Participants. Participants completing research measures include members of school mental health teams and school personnel from participating schools.

Dependent Variables and Measures

Self-Report Measures. Self-report measures of inter-professional collaboration and teamwork and feasibility and acceptability will be completed by participating mental health team members and school personnel.

Dependent measures:

Expanded School Mental Health Collaboration Instrument (ESMHCi). Mental health team members will complete the *Expanded School Mental Health Collaboration Instrument- Community version (ESMHCi-CV)*. School personnel will complete the *Expanded School Mental Health Collaboration Instrument- School version (ESMHCi-SV)*. The 59-item ESMHCi assess perceptions of three aspects of collaboration (i.e., types, influences, and benefits) between school professionals and mental health professionals from collaborating agencies on a continuous scale. Scores can be calculated individually or among groups working in the same school. For each subscale, an average score is calculated with higher scores indicating strengths and lower scores indicating areas to consider improving or targeting. Preliminary psychometric studies are promising and indicate validity and internal consistency.

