Observations. We will conduct observations in schools who implement TeamSTEPPS. For each school observation, a trained observer from the research team will observe team dynamics, service provision, and interactions among mental health providers, school personnel, and students. Observations will occur at baseline (i.e., before engagement in TeamSTEPPS), at the completion of TeamSTEPPS trainings, and for 1 school year following participation at two time points each school year (fall, spring). Observations will include detailed field notes and use of the adapted *NOTECHS* for school mental health teams.

STATISTICAL DESIGN AND POWER

Qualitative analysis. We will load all field notes and interview transcripts into NVivo for data management and analysis. Analysis will be guided by an integrated analytic approach.

Quantitative analysis. Quantitative analysis of feasibility will examine the proportion of schools who enroll/those invited and participants who attend TeamSTEPPS training/those eligible to participate in the school. We also will examine the distribution of AIM and FIM scores to quantitatively assess acceptability and feasibility, respectively.

Collaboration and teamwork are assessed observationally (i.e., *NOTECHS*) and via self-report (e.g., *ESMHCI*, *T-TPQ*). Mean total and domain scores on the *NOTECHS* will be computed for each school. Individual and school scores will be calculated for the self-report measures.

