The analytic approach consisted of three phases. First, preliminary analyses were conducted using paired t-tests to evaluate simple pre-to-post changes in the primary outcome measures: teamwork perceptions (T-TPQ), teamwork attitudes (T-TAQ), and collaboration (ESMHCI-SV). For the main analysis, we fitted linear mixed-effects regression models for each outcome variable, specifying random intercepts for participant ID to account for repeated measures and within-individual clustering. The core model included a binary post-training indicator as the primary predictor, along with the baseline value of the corresponding outcome as a covariate. To account for participant characteristics, we included a set of individual-level covariates: age, gender, race/ethnicity, education level, licensure status, professional role (clinical vs. school staff), years in the field, burnout (measured by the MBI-HSS subscales: emotional exhaustion, depersonalization, and personal accomplishment), and practice attitudes (EBPAS). These variables reflect clinician background, experience, and attitudes that may influence response to training. In parallel, we incorporated organizational-level covariates reflecting the structural and contextual features of training implementation. These included training group structure (small group, large group), school size, teacher-student ratio, building team size, and the number of team members trained. To examine whether training effects varied across these individual and organizational dimensions, we fitted comprehensive interaction models. These included all main effects plus full interaction terms between the post-training indicator and each individual- and organizational-level covariate. This allowed us to identify potential moderators of training impact and determine whether particular subgroups responded differentially to the intervention. Statistical significance was evaluated at the $\alpha = 0.05$ level.

Abbreviations

AIM	Acceptability of Intervention Measure
EBP	Evidence-based practice
EBPAS	Evidence-Based Practice Attitudes Scale
ESMHCI	Expanded School Mental Health Collaboration Instrument
FIM	Feasibility of Intervention Measure
MBI-HSS	Maslach Burnout Inventory – Human Services Scale
NOTECHS	Oxford Non-Technical Skills scale
TeamSTEPPS	Team Strategies and Tools to Enhance Performance and Patient Safety
T-TPQ	TeamSTEPPS Teamwork Perceptions Questionnaires

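### The models' only time term is one post-training indicator although two follow-ups are planned, so change that fades and change that builds can look the same

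*Combined protocol and SAP*

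**What the plan says.** The Procedure paragraph of the Protocol sets the self-report schedule: "We will collect self-report data at baseline (i.e., before engagement in TeamSTEPPS"), and then "for the school year following participation at two time points each school year (fall, spring"). That makes three occasions. The season in which baseline falls is not given. The Observations paragraph adds an end-of-training visit, but only for the observational measure.

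Under Statistical Design and Power, the main analysis fits a linear mixed model to each self-report outcome, with a "binary post-training indicator as the primary predictor" and the outcome's own baseline value as a covariate. The random part is described as "specifying random intercepts for participant ID to account for repeated measures and within-individual clustering". No wave, season or calendar-time term is listed. The moderator models add "full interaction terms between the post-training indicator and each individual- and organizational-level covariate", so they rest on the same two-level time variable. Paired t-tests of pre-to-post change come first, and the text does not say which follow-up is the post value.

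The Procedure paragraph says the exploratory outcomes will help to "identify measures that are sensitive to change for future trials". No comparison group is described.

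**The concern.** Two follow-ups at different distances from training carry information about timing: whether a change appears early, whether it lasts, and whether it takes a school year to develop. A single 0/1 term discards that information if both follow-ups are coded 1, because it forces the change from baseline to be equal in fall and spring.

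A team planning the next trial needs to know which instrument moves and when to measure it. An instrument that moves by 0.4 in fall and is back at baseline by spring calls for a different design from one that moves by 0.2 and stays there. The planned coefficient would not tell them apart. The moderator results have the same limit: a subgroup that responds early and one that responds late could show the same interaction. If attendance differs between waves, the coefficient also becomes an average whose weights depend on who responded.

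**Working it through.** **Inputs from the documents.** Three self-report occasions, one binary time term, a participant random intercept and the baseline value as covariate. The documents give no sample size, SD, effect size or power figure, so there is no planned figure to reproduce.

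**Assumptions for illustration.** Both follow-ups are coded post = 1. Baseline rows are kept as outcomes, since otherwise the indicator would be constant. Between-person SD is 0.4 and residual SD 0.3 on the 1-to-5 scale. Each pattern was simulated once with 2,000 participants, to show bias rather than power.

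**1. What the indicator estimates.** With complete data the coefficient is (fall change + spring change)/2.

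| True change, fall / spring | Post coefficient | Separate wave terms, fall / spring |
|---|---|---|
| 0.2 / 0.2 | 0.20 | 0.20 / 0.20 |
| 0.4 / 0 | 0.20 | 0.41 / -0.01 |
| 0 / 0.4 | 0.20 | 0.01 / 0.40 |
| 0.3 / -0.3 | 0.01 | 0.31 / -0.30 |

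**2. Unequal attendance.** Suppose 40% of spring responses are missing. If weights follow the number of rows, fall gets 1/(1 + 0.6) = 0.625 and spring 0.375. The fading pattern (0.4/0) then gives 0.625 × 0.4 = 0.25, and the building pattern (0/0.4) gives 0.375 × 0.4 = 0.15. The single simulation runs gave 0.27 and 0.14. Either way, two patterns with the same complete-data average of 0.20 move apart because of response alone.

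**3. Precision cost of separate waves.** Let σ be the residual SD, with n participants and complete data.
- Average of two follow-ups minus baseline: variance = σ²(1/2 + 1)/n = 1.5σ²/n.
- One follow-up minus baseline: variance = σ²(1 + 1)/n = 2σ²/n.
- Ratio of standard errors: √(2/1.5) = 1.155.

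The ratio depends on neither n nor σ. The spring-minus-fall difference also has variance 2σ²/n.

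**4. What wave coding does to season.** Let s be a recurring spring-minus-fall difference unrelated to training, and let F and S be the true changes at the two waves.

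| Contrast | Baseline in fall | Baseline in spring |
|---|---|---|
| Fall - baseline | F | F - s |
| Spring - baseline | S + s | S |
| Average - baseline | (F + S)/2 + s/2 | (F + S)/2 - s/2 |
| Spring - fall | S - F + s | S - F + s |

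Only the follow-up in the same season as baseline is free of s. The average keeps half of s whether it comes from the binary term or from the wave factor. The off-season change and the spring-fall difference carry all of it. If drift is instead common to both follow-ups, it enters both changes from baseline in full: with no training effect and a drift of -0.2 at both waves, the simulation gave -0.20 from the binary term and -0.20 from each wave term.

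**The case against.** **Pooling is inferred.** The plan never says that both follow-ups are coded 1. Pre-to-post wording also fits an analysis that uses one post wave. This stands, and the point is therefore conditional. The other reading is no better specified: the text does not say which wave is used, and the second planned wave would be left out.

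**An average change is a legitimate pilot summary.** The aim does not mention timing or durability in so many words. This stands in part. The average should stay, but the wave-specific results come from the same data at little cost, and a future trial has to choose a measurement time.

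**A stronger reading is tempting.** A reader might infer that the binary coding lets school-calendar drift pass as a training effect, and that wave terms would cure it. The documents do not support that. They give no baseline season, sample size, correlation or drift. Under one assumed set (n = 60, within-person correlation 0.5, fall baseline, spring drift of 0.2 or 0.3 SD, no training effect), the binary term rejects in 14% or 27% of simulated trials. The average from the wave model rejects in 14.5% or 28.5%, and the off-season contrast in 36% or 65%. The season-matched contrast rejects in about 5%, but only because the drift was assumed to be purely seasonal. These rates are illustrations and are not evidence for the fix. Drift that does not recur by season comes from the lack of a described comparison group, not from the coding.

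**The outcomes are exploratory.** The Procedure paragraph names feasibility and acceptability as the primary implementation outcomes. The analysis text nevertheless calls the teamwork and collaboration scales primary outcome measures and tests them at 0.05. This keeps the severity modest but does not remove the point.

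**Conclusion.** The point holds in a limited form. On the natural reading, the core and moderator models cannot separate change that fades from change that builds or stays level: three quite different patterns all give about 0.20, and a full reversal gives about zero. Uneven attendance shifts the average further. These sizes rest on the assumed effects and SDs. That the coefficient is an average follows from the coding alone, provided both follow-ups are coded as post.

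Wave coding restores the description of timing. It does not show that training caused the pattern, and a spring-fall difference may itself be partly seasonal. The season-matched contrast is a partial safeguard, against recurring seasonal differences only. This is a cheap improvement, not a flaw that invalidates the analysis.

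**What to change.** - State which waves enter each mixed model and each paired t-test, and how they are coded.
- Replace the binary indicator with a three-level wave factor (baseline, fall, spring). Keep the fall-spring average versus baseline as the summary contrast.
- Report fall minus baseline, spring minus baseline and spring minus fall with 95% CIs, and the number responding at each wave.
- State each school's baseline season and flag the follow-up in that season as the season-matched contrast. Note that the average, the off-season change and the spring-fall difference are not free of recurring fall/spring differences.
- Describe every estimate as uncontrolled pre-post change, because secular drift and regression to the mean remain whatever the coding.

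The cost is one degree of freedom, about 15% larger standard errors for the wave-specific estimates with complete data, and three more estimates per outcome from data already scheduled. The analysis section is written in the past tense, so if the models have already been fitted, the wave-specific results should be labelled as added afterwards.
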